5.2 Study Treatments Administered

5.2.1 Dose and Route of Administration

After randomization, study treatment will be started on the same date that notification of study drug identifiers is given. One tablet of DU-176b 15 mg or placebo will be administered orally once daily. Administration of the study drug will be continued until the examination at completion of study treatment performed within 60 days after the declaration of completion of the study. Completion of the study will be declared when the planned number of subjects with primary efficacy endpoint events (stroke and SEE) has been collected. The planned mean duration of study treatment is 2 to 2.5 years. When the investigator or subinvestigator requires to know the study treatment assignment for each subject to determine the subsequent treatment after the final administration of the study drug, the study treatment can be continued until the final follow-up examination (in principle, within a month after notifying their study treatment assignments) after obtaining consent from the subject. The planned duration of the additional study

treatment from the examination at completion of study treatment to the final follow-up examination is 3 to 4 months.

<Rationale>

For the DU-176b group, a dosage of 15 mg once daily was selected, so that it is expected to be effective at reducing the risk of stroke, and so that the bleeding risk is lower than that for the approved edoxaban dosage.

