result), randomization						
Study drug administration		+			→ *	→ f
Study drug compliance		+			1	
Height	← X	\rightarrow				
Physical						
examination/medical	← X	\rightarrow	X	X	X	X
interview						
Body weight	← X		X	X	X	X
Blood pressure/pulse rate	← X	\rightarrow	X	X	X	X
Hematology testg	← X		X^h	X	X	X
Blood chemistry testg	← X	\rightarrow	X^h	X	X	X
Endocrinology testg	← X	\rightarrow	X^{h}	X	X	X
Urinalysisg	← X	\rightarrow	X^h	X	X	X
CLcri	← X	←	X^h	X	X	X
12-lead electrocardiogram	← X	,	\mathbf{X}^{j}	X^k	X	X
(ECG)	$\leftarrow \Lambda$. →	N	A-	Λ	А
Head CT or MRI ^l	← X	\rightarrow				
Whether surgery or		_				
hospitalization occurred						
Adverse events		+				m
Efficacy/bleeding events		←				
Concomitant medication	←				→	
Follow-up survey after						
interruption/discontinuatio			-			
n of study drug ⁿ						
Pharmacokinetic blood						
samplingg	\sqcup		Xº			
Blood sampling for PD		X				
indicatorsg	\vdash					
Blood sampling for		X	X°			
biomarker measurementg	\vdash					
PGx banking ^p	1		← ∑	$\zeta^q \rightarrow$		

- a: Will not be performed on subjects withdrawn from the study.
- b: Will be performed in subjects who continue the study treatment, in principle, within a month after notifying their study treatment assignments.
- c: Will be calculated by taking the date of the scheduled visit to be Day 0.
- d: Falling score, frailty assessment, and one-leg standing test with eyes open will be surveyed by the time of Visit 3.
- e: Study treatment will be started on the same date that notification of study drug identifiers is given. Study treatment will be continued until the examination at completion of study treatment, which will be performed within the 60 days after the declaration of completion of the study that is made when the planned number of subjects with primary efficacy endpoint events (stroke and SEE) has been collected.
- f: The study drug will be administered only to subjects who provided consent for the additional study treatment during the period from the examination at completion of study treatment to the final follow-up examination.
- g: These will be measured at the central laboratory.
- h: Will be performed once every 8 weeks (Week 4 to Week 48: Visit 3, Visit 5, Visit 7, Visit 9, Visit 11, Visit 13/Week 48 onward: Visit 14, Visit 15, Visit 16...).
- i: Will be calculated with the Cockcroft-Gault formula.
- j: Will be performed once every 12 weeks (Visit 4, Visit 7, Visit 10, Visit 13).

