6.2 Baseline Subject Characteristics

Between the day of informed consent (Visit 0) and randomization, the following baseline subject characteristics will be surveyed and entered on case report forms.

- Date of informed consent, date of enrollment, subject number, and study drug identifier
- Demographic
 - Date of birth, age (at consent), sex, and alcohol use
- 3) Variables relating to disease and prognosis
 - Type of AF, risk factors for thromboembolism (CHADS₂ index score and CHA₂DS₂-VASc index score⁶) (whether present or not and details), HAS-BLED score⁶) (whether present or not and details), medical history (whether present or not and details), inpatient/outpatient status, history of administration of oral

anticoagulants (whether present or not and details), bleeding risk (whether present or not and details), PT-INR,* whether certified as requiring nursing care and grade of care required, falling risk (whether present or not and details), the following items will be surveyed by Visit 3 (see Appendix): falling score,²³⁾ frailty assessment,^{24),25)} one-leg standing test with eyes open ²⁶⁾

*: If the subject was receiving warfarin before informed consent was received

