6.12 Plasma Drug Concentration, Pharmacokinetic Indicators, and Biomarkers

6.12.1 Plasma Drug Concentration

6.12.1.1 Blood Sampling Times and Meal Records for Measuring Plasma Drug Concentration

Blood sampling for measurement of plasma drug concentration will be performed on Week 8 (Visit 3) of the study treatment period (see Table 6-2). The investigator or subinvestigator will instruct the subject to make a visit without receiving the morning dose of the study drug, will collect a blood sample at the trough time promptly after the subject makes a visit, and will record the date of blood sampling and time of blood sampling on the case report form. The investigator or subinvestigator will also enter the times when the study drug was administered 2 days before and 1 day before the day of blood sampling, the start times of the meals before and after the study drug was administered on the day before blood sampling, and the start times of the meals before and after the study drug was administered on the day of blood sampling. After this, the subject will receive the study drug at the study site, and a blood sample will be collected 1 to 3 hours after the study drug was administered, and the time when the study drug was administered and the time when the blood sample was collected will be entered on the case report form. If possible, a blood sample will also be collected between 4 and 8 hours after the study drug was administered, and the time when the blood sample was collected will be entered on the case report form.

Table 6-2 Times of Blood Sampling for Measuring Plasma Drug Concentration

Time of blood sampling	Remarks
Trough	Must be collected
Between 1 to 3 hours after the study drug is administered	Must be collected
Between 4 to 8 hours after the study drug is administered	Will be collected if possible

6.12.1.2 Method of Blood Sampling for Measuring Plasma Drug Concentration, Plasma Isolation, and Storage

A quantity of 5 mL of venous blood will be collected using a 5 mL vacuum blood sampling tube containing lithium heparin. Directly after sampling, the blood will be mixed by inversion and cooled. The specimen will be promptly centrifuged for 10 minutes at $1500 \times g$. The plasma will be immediately fractionated into a container for submission, and stored at the study site at no higher than -20°C , protected from light

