11.3.2 Handling of Survey and Measurement Times

The eligibility assessment period will be within the 30 days after the day of informed consent, which will be counted as Day 0. The window for surveys and measurements

for each visit will be within 14 days before or after the specified date, which will be considered Day 0. The window for the examination at completion of study treatment will be 60 days after the date of declaration of completion of the study, which will be considered Day 0. The window for the examination at discontinuation will be 7 days after the day of discontinuation, which will be considered Day 0. The window for the final follow-up will be 30 to 37 days after the day of the examination at completion of study treatment, which will be considered Day 0 (For subjects who continue the study treatment after the completion of study treatment, in principle, within a month from the day of notifying their study treatment assignments as Day 0.). If multiple measurements are made within the window, the measurements made on the day nearest to the specified day of measurement will be selected. If there are measurements before and after the specified day that are the same number of days away, the latter measurements will be selected.

Data that do not meet the handling criteria will be excluded from analysis. If there are no data that meet the handling criteria, the relevant data point will be handled as being missing.

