Appendix 2 Falling Score²³⁾

Survey the following items and enter them on the case report form.

- 1. Has the subject fallen in the past year? (yes/no) If so, how many times? (times/year)
- 11 50, now many times: (times/year)
- 2. Does the subject sometimes trip or stumble? (yes/no)
- 3. Can the subject ascend or descend stairs without holding a handrail? (yes/no)
- 4. Has the subject's walking speed decreased? (yes/no)
- 5. Can the subject finish crossing the road at a pedestrian crossing while the signal is green? (yes/no)
- 6. Can the subject continue walking for about 1 kilometer without a break? (yes/no)
- 7. Can the subject stand on one leg for about 5 seconds? (yes/no)
- 8. Does the subject use a cane? (yes/no)
- 9. Can the subject wring out a towel? (yes/no)
- 10. Does the subject have dizziness or faintness? (yes/no)
- 11. Does the subject have a stooped or rounded back? (yes/no)
- 12. Does the subject have knee pain? (yes/no)
- 13. Does the subject have visual disturbance? (yes/no)
- 14. Does the subject have hearing disturbance? (yes/no)
- 15. Does the subject have forgetfulness that concerns him/her? (yes/no)
- 16. Is the subject anxious about the possibility of falling? (yes/no)
- 17. Does the subject receive 5 or more drugs every day? (yes/no)
- 18. Does the subject experience a sensation of darkness at home? (yes/no)
- 19. Are there obstacles that the subject must avoid in the corridor, living room or entryway? (yes/no)
- 20. Are there steps in the subject's house? (yes/no)
- 21. Does the subject have to use steps? (yes/no)
- 22. Does the subject walk along steep slopes near to his/her home in his/her daily life? (yes/no)

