Appendix 3 Frailty Assessment^{24),25)}
Survey the following items and enter them on the case report form.

Item	Details	
Weight loss	If the subject answers "yes" to the question "Have you (unintentionally) lost 2 to 3 kg or more in the past 6 months?"	
Exhaustion	If the subject answers "yes" to the question "In the last 2 weeks, have you felt tired for no reason?"	
Activity level	If the subject answers "I do not do exercise" to both of the following questions: Approximately how many days per week do you engage in low levels of physical exercise (including farm work)? Approximately how many days per week do you engage in moderate levels of physical exercise or sports (including farm work)?	
Grip strength	(Measured in the dominant hand) < 26 kg for men or < 18 kg for women	
Comfortable walking speed	(Measure the time taken to walk a measurement section with a length of 5 m, with a lead-in section of 1 m before and after the measured section.) If the speed is < 1 m/s.	

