Appendix 4 One-leg Standing Test with Eyes Open²⁶
Conduct a test according to the following procedure, and enter the results of the test on the case report form.

1. Preparation

Stopwatch

2. Method

- I. The subject is to take the test in bare feet.
- II. The subject places both hands on his/her hips, and stands on one leg at a time, trying each leg to check which one is easiest to stand on.
- III. When the subject has chosen a leg to stand on, he/she puts his/her hands on his/her hips, and upon being told to "raise one leg," assumes a one-legged stance.

Records

- Measure the duration of the time for which the subject maintains the one-legged stance. End the test if the subject continues to maintain the one-legged stance for 120 seconds.
- II. Record times in seconds, rounding down fractions of a second.
- III. Conduct the test twice and record the better score out of the two tests. (If the first result is 120 seconds, do not conduct the test a second time.)
- 4. Precautions about conducting the test.
 - I. Conduct the test on a non-slip floor.
 - II. Do not place objects near the subject undergoing the test. Avoid locations with stairs or slopes.
 - III. Before the test, inform the subject undergoing the test of the following.
 - A) The task in this test is to stand on one leg for as long as possible.
 - B) The stance for standing on one leg is to keep the knee of the supporting leg straight, and raise the other leg up so that it does not touch the supporting leg.
 - C) The conditions for ending the test are:
 - i. If the leg being lifted up touches the ground or the supporting leg
 - ii. If the position of the supporting leg shifts
 - iii. If the subject takes one or both hands off his/her hips.
 - D) Since saying "start" is enough to make some people lose their balance, it is

- better to start by saying "raise one leg" and measure the time starting from when the subject stands on one leg.
- E) The person doing the measurement will be ready to support the subject undergoing the test immediately if he/she loses his/her balance.
- F) The conditions for ending the tests will be strictly adhered to. It is advisable to allow the subject undertaking the test to practice first.

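### Does allowing the falling score, frailty assessment and one-leg stand up to Visit 3 spoil them as baseline characteristics?

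*Combined protocol and SAP*

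**What the plan says.** Section 6.2 sets the general rule for baseline data: "Between the day of informed consent (Visit 0) and randomization, the following baseline subject characteristics will be surveyed". Under its heading for disease and prognosis variables, the same list then names the falling score, the frailty assessment and the one-leg standing test and gives them until Visit 3. Footnote d, in both the synopsis schedule and Table 6-1, repeats this: "Falling score, frailty assessment, and one-leg standing test with eyes open will be surveyed by the time of Visit 3".

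The timing follows from three other places.

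- Section 6.12.1.1 fixes Visit 3: "Blood sampling for measurement of plasma drug concentration will be performed on Week 8 (Visit 3) of the study treatment period".
- Section 11.3.2 says that the measurement window "for each visit will be within 14 days before or after the specified date".
- Section 5.2.1 fixes the start of dosing: "After randomization, study treatment will be started on the same date that notification of study drug identifiers is given".

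On recording, Appendices 2 and 3 ask for the items to be entered, and Appendix 4 says: "Conduct a test according to the following procedure, and enter the results of the test on the case report form". None of them mentions the date of assessment.

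On use, section 11.4.1 tabulates baseline characteristics by group. Section 11.4.2.4 plans subgroup analyses of the primary endpoint by major baseline characteristics and leaves the list to the Statistical Analysis Plan. Section 11.4.2.1.1 adjusts the primary Cox model for CHADS₂ score and lets blinded review add factors.

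**The concern.** A baseline variable should be fixed before treatment can affect it. Here a value can carry that label although it was taken weeks after the first dose, possibly after a stroke or a bleed. Grip strength, walking speed and one-leg stance are measured on the day, and a stroke can change all three. The exhaustion item asks "In the last 2 weeks, have you felt tired for no reason", so at Week 8 its whole recall period lies on treatment. A subject could then be classed as frail because of the outcome and placed in a frail subgroup. A subject who dies or withdraws early may have no value at all, and section 11.3.3 imputes nothing.

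The recording instructions add to the worry. Section 6.7.1 asks for the date on which height was measured, and the sections on head imaging, ECG, weight and blood pressure likewise ask for dates. For these three items no date is stated, and no rule separates pre-dose from post-dose values. The by-group baseline tables, any subgroup built on these items, and any covariate added at blinded review could be affected.

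**Working it through.** **The plan's own figure.** Section 11.6 gives 65 events for hazard ratio 0.5, two-sided 5% and 80% power. With the Schoenfeld formula and 1:1 allocation, D = 4 × (1.960 + 0.842)² / (ln 0.5)² = 65.3. At 65 events the power is 79.8%. The figure is reproduced, and the timing of these items does not alter it.

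**Latest date of assessment.** Week 8 is Day 56. With 14 days either side, Visit 3 falls between Day 42 and Day 70, so the latest value comes about 10 weeks after the first dose.

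**Events before the assessment, worst case.** Inputs from section 11.6: placebo 5%/year, DU-176b 0.5 × 5% = 2.5%/year, 400 per arm. Assumptions: exponential times, no dropout, every subject tested at the deadline. With t = days/365.25, the expected number in an arm is 400 × (1 − exp(−rate × t)).

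| Deadline | Placebo | DU-176b | Total | Share of 65 events | Share of 800 subjects |
|---|---|---|---|---|---|
| Day 56 | 3.05 | 1.53 | 4.58 | 7.1% | 0.57% |
| Day 70 | 3.81 | 1.91 | 5.73 | 8.8% | 0.72% |

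The ratio between arms is 1.53/3.05 = 0.50 and 1.91/3.81 = 0.50, the planned hazard ratio. Early events therefore carry no expected shift in the treatment effect.

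**Major bleeds before the assessment.** At the 1.99%/year that sections 1 and 5.2.1 cite for 15 mg at age 80 or older, the DU-176b arm would have 400 × (1 − exp(−0.0199 × t)) = 1.2 by Day 56 and 1.5 by Day 70. The protocol gives no placebo rate for bleeding.

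**How much of each question is post-dose at Day 56 to Day 70.**

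- Exhaustion, 2-week recall: 14/14 = 100%.
- Weight loss, 6-month recall: 56/182.6 = 31% to 70/182.6 = 38%.
- Falls, where Appendix 2 asks "Has the subject fallen in the past year": 56/365.25 = 15% to 70/365.25 = 19%.
- Home-environment items in Appendix 2: hardly any.
- Falling risk (Appendix 1) and nursing-care grade: none, since section 6.2 keeps them under the pre-randomization rule.

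**Where the values are used.** The randomization stratum is CHADS₂ score (section 5.2.2.1). The planned covariate is CHADS₂ score (section 11.4.2.1.1). None of the three items appears among the endpoints in sections 7 to 10, and no subgroup is named. The one certain route by which they could appear is the descriptive table of section 11.4.1.

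**The case for a change.** The best case for a change is that it would be cheap and that the items matter in this population. Section 1 counts falling risk among the reasons why anticoagulation is thought unsuitable, and section 6.2 files the items with the prognostic variables, so they are plausible subgroup factors. Subgroup estimates rest on few events, and several misclassified subjects could count there. Late collection may be practical, but no reason is given, and a deadline does not turn a post-dose value into a baseline one. Section 11.3.2 also leaves a gap: a value taken on Days 1 to 13 falls before the Week 4 window (Days 14 to 42) and outside the eligibility period, so its status is undefined.

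The timing, the silence on dates and the missing rule all stand. The need for a change does not, for four reasons.

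- **Date.** The case report form and its entry guide (section 15.9.2) are not part of the document. The general recording instruction in section 6.1 gives examples rather than a full list, and section 6.2 states no assessment date for most of its other surveyed items either. One can say that no date is stated, not that none is collected.
- **Rule.** Sections 11.3.1 and 11.4.6 provide for decisions on matters left open at planning, and section 5.2.2.4 requires data handling to be final before unblinding. A convention for these items, including the early gap, can be set there.
- **Covariate route.** An item would have to be tested late, be altered by an early event, look prognostic in blinded review and then be added. Section 11.5 sends changes to the primary analysis through protocol amendment.
- **Remedies.** Earlier testing would reach few or no subjects: the study began in May 2016, section 11.6 assumes 2 years of enrollment, and this version dates from May 2019. Removing every post-dose value from baseline, with no imputation, could discard slow-changing and largely valid answers from many subjects to guard against about five.

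**Conclusion.** No change is needed. The late window is a deliberate exception, stated in the synopsis schedule, Table 6-1 and section 6.2, and anyone building the tables is told of it. If every subject were tested at the deadline, 0.6% to 0.7% would have had a primary event first. The true share is lower to the extent that sites test earlier, and a fatal event leaves a missing value rather than a misleading one. The event target, the CHADS₂-adjusted Cox model and the expected hazard ratio are unaffected, and double-blinding keeps knowledge of treatment out of the measurements.

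This rests on the section 11.6 event rates with constant hazards, and on no section assigning the items an inferential role. The detailed subgroup list was not available to check. If one of the items does become a subgroup factor, an analyst would ordinarily footnote its timing and check the result without values dated after a stroke, systemic embolism or major bleed. That is normal analytic practice within the existing plan.

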6.2 Baseline Subject Characteristics

Between the day of informed consent (Visit 0) and randomization, the following baseline subject characteristics will be surveyed and entered on case report forms.

- Date of informed consent, date of enrollment, subject number, and study drug identifier
- Demographic
 - Date of birth, age (at consent), sex, and alcohol use
- 3) Variables relating to disease and prognosis
 - Type of AF, risk factors for thromboembolism (CHADS₂ index score and CHA₂DS₂-VASc index score⁶) (whether present or not and details), HAS-BLED score⁶) (whether present or not and details), medical history (whether present or not and details), inpatient/outpatient status, history of administration of oral

anticoagulants (whether present or not and details), bleeding risk (whether present or not and details), PT-INR,* whether certified as requiring nursing care and grade of care required, falling risk (whether present or not and details), the following items will be surveyed by Visit 3 (see Appendix): falling score,²³⁾ frailty assessment,^{24),25)} one-leg standing test with eyes open ²⁶⁾

*: If the subject was receiving warfarin before informed consent was received

6.3 Study Drug Compliance

From the initial dose of study drug date (the same date as the date of notification of the study drug identifier) to the examination at completion of study treatment or the examination at discontinuation, the medical interviews will be performed and study drug compliance (number of tablets administered) will be determined from the remaining drug collected from subjects. The following information will be entered on case report forms: whether study treatment was administered, the date of the start of treatment, the date of completion of treatment, whether study drug interruption occurred, date of study drug interruption, date of study drug resumption, and the reasons for study drug interruption.

